Other end-points of outcome measures	
 
— Composite of death from any cause, non-fatal myocardial infarction, stroke, or major bleeding within a 12-month of the study follow-up (Net adverse clinical events - NACEs);
 
— Composite of death from any cause, non-fatal myocardial infarction, or stroke within a 12-month of study follow-up (Major adverse cardio or cerebrovascular events - MACCEs);
 
— Composite of death from cardiovascular cause, non-fatal myocardial infarction, recurrent angina, or repeated revascularization (PCI or CABG) within a 12-month of study follow-up (Major adverse cardiovascular events - MACEs);
 
— Number of study participants whose health status was defined as good or satisfactory, or with the appearance of CVD symptoms, or with a significant inability to self-care (Patient-Reported Health Status) reported by the patient or patient caregiver at 3, 6 and 12 months of the study follow-up;
 
— Participants self-reported (or patient's caregiver reported) angina not required hospitalization (Patient-Reported Angina Not Required Hospitalization at 3, 6 and 12 months of the study follow-up;
 
— Participants reported (or patient's caregiver reported) last week's shortness of breath due to heart failure not requiring hospitalization (Patient-Reported Heart Failure Severity) at 3, 6 and 12 months of the study follow-up;
 
— Withdrawal for any reason within a 12-month of the study follow-up;
 
— Costs of clinical service utilization for case management during the study follow-up;
 
— Incremental costs incurred for real-world health care services, including costs for the MACCEs, MACEs and NACEs;
 

Other measures	
 
— Cardiometabolic risk factors and their control status;
 
— Total number of hospitalizations for any reason within 12 months of the study follow-up;
 
— Comorbidities;
 

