- Number of study participants who experienced major bleeding (Major Bleeding) within a 12-month of the study follow-up;

- Number of study participants who experienced non-major bleeding (Non-major Bleeding) within a 12-month of the study follow-up;
- Number of study participants who experienced a heart failure event (Heart Failure Event) within a 12-month of the study follow-up;
- Number of study participants who experienced percutaneous coronary intervention or coronary artery bypass-grafting (Repeated Coronary Revascularization) within a 12-month of the study follow-up;

Pre-specified endpoints of the study are defined as:

- Number of study cases in each arm with a composite of death from any cause, myocardial infarction, stroke, or major bleeding (Net adverse clinical events - NACEs) within a 12-month of the study follow-up;
- Number of study cases in each study arm with a composite of death from any cause, myocardial infarction, or stroke (Major adverse cardiac or cerebral events - MACCEs) within a 12-month of the study follow-up;
- Number of study participants who reported their health status as good or satisfactory, or with the appearance of CVD symptoms, or with a significant inability to self-care (Patient-Reported Health Status) at 3, 6 and 12 months of the study follow-up;
- Number of study participants self-reported angina not required hospitalization (Patient-Reported Angina Not Required Hospitalization) at 3, 6 and 12 months of the study follow-up;
- Number of study participants reported last week's shortness of breath due to heart failure not requiring hospitalization (Patient-Reported Heart failure Severity) at 3, 6 and 12 months of the study follow-up;
- Number of study participants withdrawn from the study for any reason within a 12-month of the study follow-up;
- Costs of clinical service utilization for case management during the study follow-up;
- Costs incurred for incremental services, including costs for the major adverse cardiovascular and cerebrovascular event;

Along with studying the effectiveness of CYP2C19 genotype-guided treatment selection with clopidogrel and an alternative P2Y12 inhibitor, clinical case management processes in the real-life healthcare system and factors that positively and negatively impact the processes will be evaluated: healthcare processes, place of care, delivery of medical procedures, medication use, and management of comorbidities.

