### **3.2.6 Adverse Event Reporting**

Any MACCE or AAME observed or voluntary adverse event occurring in a trial is identified by the investigator or sponsor. Information about it is submitted to the trial participant's medical care team, who should then direct the clinical case management.

A MACCE or AAME event is recorded:

- In the study data registration form;
- A description and significance of the event are recorded in the routine medical documentation;

After the registration of the MACCE or AAME event, the participant will be withdrawn from the study.

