## **3.3 Early Withdrawal of a Study Participant**

A study participant may withdraw from the study at any time during the study and for any reason, whether identifiable or not, by their own free will. This decision and the patient's independent choice are presented in the informed consent form.

A study participant may also be withdrawn early from the study if there is persistent non-adherence to the study follow-up and treatment procedures (see Chapter 2.5.6, Withdrawal from the Study Due to Non-Adherence to Treatment).

A study participant may be withdrawn early from the study based on a clearly stated justification by the investigator or the study sponsor if it is in the patient's best interests to discontinue the study.

The basic reasons for withdrawal from the study are considered as follows:

- If any abnormal study result, symptom, or measurement parameter is detected and resolution, improvement, correction or stabilization of which may require a long period of treatment and/or observation and will change the course of the study-defined follow-up and treatment;
- Any adverse event that may persist during the follow-up period, or require a change or discontinuation of the study-defined treatment, or disrupt the study-defined clinical evaluation plan, or be associated with a severe outcome.
- Any adverse event that may be masked by the use of different medical care regimens than those specified in the study protocol;
- If study treatment intervention, it may pose an expected AAME, a health threat, requiring discontinuation and modification. These conditions require modified treatment measures and regimens other than those specified in the study, including hospitalization. In addition, clinical conditions that may be characteristic of AAME may be exclusion criteria from the study.
- An adverse event related to treatment with P2Y12 inhibitors is a study endpoint, after which the study-planned follow-up is no longer required.
- The MACCE determines the study endpoint, and further measures are no longer required.

In these cases, study participants are discontinued from the study-planned follow-up; the necessary assessments of early withdrawal from the study should be conducted, and the reason for early withdrawal from the study should be determined (evaluated). In these cases, the patient continues to be monitored and treated by the medical support team.

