
Costs associated with the utilization of medical care services of real-world clinical practice in the 'unspecified metabolizer' study arm cases (in USD, <math>m \pm Std</math>)
	
Calculating: Mean value of the costs (<math>m</math>) and standard deviation (<math>Std</math>) in the 95% confidence interval

Difference in costs associated with the utilization of medical care services of real-world clinical practice between 'normal metabolizer' study participants' arm vs 'unspecified metabolizer' study participants' arm
	
Measuring: Statistical significance of the difference between the means two study arms in the 95% confidence interval by <math>p</math> value using Student's Two-sample t-test

Difference in costs associated with the utilization of medical care services of real-world clinical practice between aggregated 'normal metabolizer' and 'passive metabolizer' study participants' arms vs 'unspecified metabolizer' study participants' arm
	
Measuring: Statistical significance of the difference between the means two study arms in the 95% confidence interval by <math>p</math> value using Student's Two-sample t-test

Incremental costs associated with the utilization of medical care services of real-world clinical practice in the study cases manifested MACCEs (in USD, <math>m \pm Std</math>)	Calculating: Mean value of the costs ( $m$ ) and standard deviation ( $Std$ ) in the 95% confidence interval
Incremental costs associated with the utilization of medical care services of real-world clinical practice in the 'normal metabolizer' study arm cases manifested MACCEs (in USD, <math>m \pm Std</math>)	Calculating: Mean value of the costs ( $m$ ) and standard deviation ( $Std$ ) in the 95% confidence interval
Incremental costs associated with the utilization of medical care services of real-world clinical practice in the 'passive metabolizer' study arm cases manifested MACCEs (in USD, <math>m \pm Std</math>)	Calculating: Mean value of the costs ( $m$ ) and standard deviation ( $Std$ ) in the 95% confidence interval
Incremental costs associated with the utilization of medical care services of real-world clinical practice in the 'unspecified metabolizer' study arm cases manifested MACCEs (in USD, <math>m \pm Std</math>)	Calculating: Mean value of the costs ( $m$ ) and standard deviation ( $Std$ ) in the 95% confidence interval

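### The total-cost endpoint has no explicit fixed window and can be cut short by event-triggered withdrawal, so the crude comparison of mean cost between arms is biased

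*Combined protocol and SAP*

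**What the plan says.** The Synopsis (Other end-points of outcome measures) lists two cost endpoints. The first is "Costs of clinical service utilization for case management during the study follow-up", and section 2.6.1 repeats it. The second is "Incremental costs incurred for real-world health care services, including costs for the MACCEs, MACEs and NACEs"; in section 2.6.1 it reads "Costs incurred for incremental services, including costs for the major adverse cardiovascular and cerebrovascular event". Only the first is tied to study follow-up. Neither states a 12-month period, although neighbouring clinical endpoints do.

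On when follow-up ends:

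- Section 3.2.6: "After the registration of the MACCE or AAME event, the participant will be withdrawn from the study".
- Section 3.3: "The MACCE determines the study endpoint, and further measures are no longer required". In the cases it lists, "study participants are discontinued from the study-planned follow-up". Data collected up to withdrawal are used.
- Section 3.4: a participant's study period is 12 months, but may be shorter after early withdrawal.
- Section 3.2.1: the triggers are broad. MACCE includes recurrent angina, TIA and atrial fibrillation. AAME includes minor bleeding and a change or stop of the P2Y12 inhibitor.

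Appendix 3 has 24 cost rows: six for total cost and six each for incremental cost in MACCE, MACE and NACE cases. They are means with standard deviations, or two-sample t-tests, such as the row that begins "Difference in costs associated with the utilization of medical care services of real-world clinical practice between aggregated 'normal metabolizer' and 'passive metabolizer" and compares the pooled guided arms with the ungenotyped arm. No row states a window or a rule for participants observed for less than 12 months. Section 2.4.2 expects 75% to complete follow-up.

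**The concern.** If follow-up stops when an event is registered, the length of cost observation depends on the outcome. An arm with more events then contributes fewer months of routine cost, and it may lose part of the cost of the events themselves. A crude mean treats these shortened totals as complete.

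At stake is the economic reading of the trial. A strategy that prevents events keeps more participants under observation for the full year and so accrues more routine cost, while some of the cost it avoids goes unrecorded in the other arm. The distortion follows event counts, not arm labels. Section 1.3 expects more bleeding with the newer agents, and bleeding is also a withdrawal trigger, so the guided arms could be the ones truncated more.

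**Working it through.** The documents contain no unit cost, cost standard deviation or cost-based sample size, so there is no stated cost figure to reproduce. The check is an algebraic model, and all its cost inputs are assumptions.

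**Inputs**
- Event probability p by 12 months. Section 3.2.1 gives 1–10% for MACCE; section 2.6.2 plans on up to 0.4 in the experimental arm and up to 0.6 in control. The 10% v 5% split used below is assumed.
- Events are non-fatal and uniform over 12 months, so they fall at month 6 on average (assumed).
- Routine cost is c per month and continues unchanged after an event (assumed).
- Event cost is E, of which a share f is recorded before withdrawal (unknown).

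**Observation time**
Mean observed months = 12 − 6p. This gives 11.94 at 1%, 11.4 at 10%, 9.6 at 40% and 8.4 at 60%.

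**Mean cost per participant**
- Truncated at the event: (1 − p)·12c + p·(6c + fE)
- Full 12 months: (1 − p)·12c + p·(6c + E + 6c) = 12c + pE

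**Arm difference** (more-event arm minus fewer-event arm, with risk difference Δp)
- Full: Δp·E
- Truncated: Δp·(fE − 6c)
- Understatement: Δp·[(1 − f)E + 6c]

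Even at f = 1, each extra event leaves 6c uncounted. The sign reverses when fE < 6c, whatever the event risks. With a mean event time of t months, the threshold becomes fE < (12 − t)c.

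**Results, in months of routine cost (c = 1)**

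| Event risks | E | Full | f = 0 | f = 0.5 | f = 1 |
|---|---|---|---|---|---|
| 10% v 5% | 6 | 0.30 | −0.30 | −0.15 | 0.00 |
| 10% v 5% | 12 | 0.60 | −0.30 | 0.00 | 0.30 |
| 10% v 5% | 24 | 1.20 | −0.30 | 0.30 | 0.90 |
| 60% v 40% | 12 | 2.40 | −1.20 | 0.00 | 1.20 |
| 60% v 40% | 24 | 4.80 | −1.20 | 1.20 | 3.60 |

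One case was simulated with 2,000,000 draws per arm (60% v 40%, E = 12, f = 0.25). Truncated means were 10.20 and 10.80, a difference of −0.60. Full means were 19.20 and 16.80, a difference of +2.40. Both agree with the formulas.

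**Follow-up after an event**
The sections do not agree. Section 3.2.6 makes withdrawal automatic. Section 3.2.7 lets the IRB recommend either further follow-up or withdrawal. Section 3.2.3 follows adverse effects until they resolve or stabilise acceptably. Section 3.3 says nothing more is needed after a MACCE. The actual end of cost observation is therefore undefined, and so is f.

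**The case against.** The strongest reply is that the cut-off may be softer than section 3.2.6 suggests. The Synopsis provides an evaluation within 72 hours of early withdrawal. Section 3.2.2 has the investigator retrieve records of care given elsewhere, and section 7.1 makes the medical record, including outside care, the primary source. Withdrawal follows registration of an event, not its onset, so an event discovered at a scheduled visit may have its whole admission already on record. The Synopsis also sets a 12-month follow-up period and counts hospitalisations over 12 months, so a 12-month cost window is a plausible intention.

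Much of this stands, and it rules out two stronger readings. A reader might infer that costs are counted only up to the event. That does not hold, because the incremental-cost endpoint carries no follow-up limit. A reader might also infer that the plan cannot measure event costs. That is not shown: f is unknown, and nothing in the documents fixes it at a low value. What remains is that no section gives a collection period or source for cost after withdrawal, and none provides for cost to month 12.

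Two further points are fair. Death ends cost in reality, so truncation there is not bias. And continued follow-up after events would remove most of the problem, though the window and the handling of true loss would still need stating.

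**Conclusion.** The concern holds in this form: the total-cost endpoint lacks an explicit fixed window, its observation period can end at event-triggered withdrawal, and the planned crude comparison ignores unequal observation. For non-fatal events, cost in the arm with more events is understated by (1 − f)E + 6c per event under the assumptions above. If routine cost rises after an event, the understatement is larger.

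It is tempting to conclude that the cost result will change sign. The documents do not support that. Reversal needs the captured event cost to fall below the routine cost of the months lost, about six months if events fall at month 6 on average, and no cost data are given to judge this. It is easier to meet for cheap triggers such as a minor bleed. Where fE exceeds 6c, the more-event arm still looks dearer, by too little. At 10% event risk the loss of routine cost time is 0.6 of 12 months, or 5%; at the sample-size rates it is far larger.

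Nor do the documents call cost the main non-clinical outcome. It comes last among the other endpoints. This is a worthwhile and cheap correction to a lower-tier endpoint.

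**What to change.** 1. Define both cost endpoints (Synopsis and section 2.6.1) and all Appendix 3 cost rows over 12 months from one stated origin for every randomised participant, regardless of withdrawal from visits or an endpoint event, subject to consent. The origin can be randomisation or the start of the intervention, from which the Synopsis counts follow-up.
2. Name the medical record described in section 7.1 as the cost source after visits stop, and include the event admission and later care within the window.
3. Count death as a true end of cost.
4. Treat cost as censored only for true loss to follow-up or withdrawn consent to records, and estimate the mean with a censored-cost method such as inverse-probability-of-censoring weighting.
5. Reconcile sections 3.2.3, 3.2.6, 3.2.7 and 3.3 on follow-up after an event. The cost window above can be applied however they are reconciled.

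The price is some extra record abstraction to month 12 for withdrawn participants, and consent wording that allows record review after visits stop. Whether the present consent form already allows this cannot be judged from the text available. Treatment is not affected.

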Sample size	
The sample size for the study was determined to be 240 patients.
 
Calculations were made using two instruments that provided two approximate sample sizes. The median of these values (considering that the better the odds ratio could be achieved from the larger the sample size) was taken as the sample size.
 
(1) Calculate the sample size for scientific studies using a standard numerator based on the proportion of the population that is likely to have the demographic characteristics of the study sample and the size (number) of the population with the clinical characteristics expected for the study, with a 95% confidence level and a <math>\pm 5\%</math> confidence interval for the results of the statistical calculations.

	
(2) Sample size calculation for a randomized, parallel case-control study with a two-sided statistical significance level, at a confidence interval of <math>\alpha = 0.05</math>, at statistical power of <math>(1-\beta) = 0.8</math>, at case/control ratio of 2, at probability of occurrence of an event in the experimental arm of <math>p_0</math> – up to 0.4, and at probability of occurrence of an event in the control arm of <math>p_1</math> – up to 0.6.

Data processing	
The study data will be processed in stages when:
 
I - More than 50% of patients are enrolled in the study;
 
II - The study group is fully formed, and by this time, more than 50% of patients have completed the 3-month observation period, and some patients have completed the 6-month observation period.
 
III - all patients included in the study have completed the 6 months, and some have completed the 12 months;
 
IV - All patients included in the study have completed the 12-month observation period.
 
The following will be carried out during the follow-up periods:
 

— Observation of MACCEs and collection of information about them;

— Monitoring and evaluation of the project;

— Observation and analysis of study activities, procedures, non-clinical outcomes and safety data.

## 1.0 Study Aim

### 1.1. The Investigational Product

The investigational product is a P2Y12 inhibitor treatment selection assay based on the CYP2C19 allele genotype.

The development of the investigational product is based on assessing resistance to clopidogrel treatment by RT-PCR-based detection of impaired/non-functional alleles of the human cytochrome P450 system 2c19 enzyme encoded by the CYP2C19 \*2, \*3.

The CYP2C19 \*2, \*3 wild-type (wt) and mutant (mut) alleles will be determined, and heterozygous or homozygous carriers of CYP2C19 \*2, \*3 normal alleles or altered alleles will be determined.

Clopidogrel CYP2C19 metabolism phenotypes are determined according to the rule provided in the table below.

Alleles	Haplotypes		Test results	Metabolizing Phenotypes of the CYP2C19 Gene	
	wt	mut		Active	Passive
CYP2C19 *2	✓	—	wt/wt	▪ Normal Function Alleles; → CYP2C19 *2 wt/wt and *3 wt/wt	▪ Loss of Function alleles (Heterozygous) → CYP2C19 *2 wt/wt and *3 wt/mut or → CYP2C19 *2 wt/mut and *3 wt/wt or → CYP2C19 *2 wt/mut and *3 wt/mut
	✓	✓	wt/mut		
	—	✓	mut/mut		
CYP2C19 *3	✓	—	wt/wt	▪ Normal Function Alleles; → CYP2C19 *2 wt/wt and *3 wt/wt	▪ Loss of Function alleles (Homozygous) CYP2C19 *2 wt/wt and *3 mut/mut or → CYP2C19 *2 mut/mut and *3 wt/wt or → CYP2C19 *2 mut/mut and *3 wt/mut or → CYP2C19 *2 wt/mut and *3 mut/mut or → CYP2C19 *2 wt/mut and *3 mut/mut
	✓	✓	wt/mut		
	—	✓	mut/mut		

### 1.2. Anticipated Use of the Investigational Product

The investigational product can be used for CYP2C19 \*2, \*3 genotype-guided clopidogrel or an alternative P2Y12 inhibitor treatment of high-risk ASCVD patients for tailoring antiplatelet therapy to optimize the prevention of MACCE.

### 1.3. Relevance of the Study

Despite the progress of modern health systems, ASCVD remains the leading cause of global disease burden and mortality [1, 2]. The dramatic nature of the situation is due to the development of MACCEs in the course of ASCVD. Through complex interactions with genetic and other multiple risk factors and comorbid conditions, the disease/conditions exacerbate structural and functional disorders, manifest different clinical phenotypes of the disease, and affect treatment efficacy and outcomes [3].

Current evidence presents preventive treatment approaches for recurrent MACCEs in ASCVD, the implementation of which in routine practice allows for patient-specific and personalized clinical decisions and, as a result, improved outcomes. The pharmacotherapeutic approach to the prevention of MACCEs in CAD [4, 5] involves the routine use of aspirin and a P2Y12 inhibitor (clopidogrel, ticagrelor, or prasugrel) as part of DAPT based on a risk-benefit assessment. Current recommendations also provide a choice between newer and more potent P2Y12 inhibitors (ticagrelor and prasugrel) and clopidogrel to optimize their use at different stages of CAD management.

Nevertheless, clopidogrel remains the most commonly used P2Y12 inhibitor, including in the primary and post-elective PCI period [6]. This trend is supported by the significant risk-benefit of the use of new-generation antiplatelet agents and the higher risk of other, non-MACCEs, and adverse clinical events, such as bleeding [7].

To increase the effectiveness of clopidogrel and optimize the use of alternative, new-generation P2Y12 inhibitors, models for assessing the pharmacogenetic feasibility of drug treatment are currently being introduced into practice [8]. The hypothesis, which has been actively discussed over the past decade, that the decision to treat with clopidogrel for the prevention of MACCE is significantly more effective in meeting risk reduction goals if it is based on the results of CYP2C19 allele genotyping, is now supported by reliable clinical evidence [9-16]. Therefore, clopidogrel has become a suitable target for pharmacogenetic evaluation of P2Y12 inhibitor use, as its effects are influenced by the variability of CYP2C19 genotype in the population, which, even with conventional treatment with clopidogrel, significantly increases the risk of MACCE, especially in carriers of non-functional alleles [17].

The current paradigm for clopidogrel use faces a dilemma. Existing practice guidelines (ESCARDIO, 2017 and ACC/AHA, 2016) provide recommendations for the use of clopidogrel or other P2Y12 inhibitor treatment without CYP2C19 genotyping. A larger evidence base supporting the efficacy of the pharmacogenetic approach is required to guide treatment recommendations based on CYP2C19 genotyping, including genome-wide associations between CYP2C19 genotype variability and MACCE of recurrent ASCVD on clopidogrel treatment [8, 10]. On the other hand, the 2019 Global Consensus Report of the industry associations presented the possibility of tailoring P2Y12 inhibitor treatment based on CYP2C19 genotype and general recommendations for the selective use of CYP2C19 genetic testing [10]. The FDA's so-called "Clopidogrel" "Black box warnings" [18], EMA precautionary statements, CPIC and DPWG scientific reports [19-21], as well as the evidence base from new pragmatic and prospective studies [9-16], support the approach of CYP2C19 allele-specific P2Y12 inhibitor treatment and determine its efficacy. Approximately 30% of the European population and 60% of Asians carry CYP2C19 non-functional alleles [21], which are associated with resistance to clopidogrel treatment and a significantly increased risk of MACCE [21-24].

At this stage, the directions of scientific development can be determined by the following research questions: Can CYP2C19 allele genotypes be routinely used for P2Y12 inhibitor treatment? The answer to the main question will make a significant contribution to resolving this issue: Are CYP2C19 genetic variations associated with clinical outcomes of clopidogrel treatment independent of interactions with other known factors?

